Aim 1) to examine if patients randomly assigned to a brief overdose prevention intervention report reduced overdose risk behaviors (e.g., higher dose, concurrent alcohol use, concurrent other drug/medication use, returning to normal dose after breaks in use) over one year of follow-up compared to patients assigned to equal attention EUC.

Aim 2) to examine if patients randomly assigned to a brief overdose prevention intervention have lower total quantities of opioids prescribed (from pharmacy fill records) and aberrant opioid use (e.g., using for reasons other than pain, obtaining opioids from someone other than primary provider) over one year of follow-up compared to patients assigned to equal attention EUC.

The study will include two **secondary aims**: **1)** to examine if patients randomly assigned to the brief intervention have fewer non-fatal overdoses and other medication-related adverse events (emergency department visits, over-sedation, injuries), better functioning, and more often store and dispose of opioids safely compared to patients assigned to EUC; and **2)** to examine mediators (motivation and self-efficacy) and moderators (OIF/OEF/OND status, baseline mental health) of intervention effects.

The proposed POST study will increase our understanding of strategies to reduce adverse outcomes related to prescription opioid use, namely, risk of overdose, among VHA primary care patients. This study is the next logical step in addressing the risks of prescription opioid use among VHA patients, providing critical, initial data to inform VHA clinicians to prevent adverse opioid-related outcomes. Knowledge generated from

this pragmatic trial is likely to have broad implications for improving safe opioid use, the enhancement of PC-MHI services, and the quality of pain care for current and future VHA patients.

BACKGROUND

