Demographics Information on participants' race, gender, sexual orientation, OEF/OIF/OND status (MSI), marital status, employment status, income, and education will be collected. Contact information and housing status, address, phone number, e-mail (if applicable) and type of living arrangement will also be collected.

Analysis plan. The project's data management and analysis will be supervised by [name], who received advanced biostatistics training during her Ph.D. in public health. Tests for linearity, independence, missingness, and distributional assumptions will be conducted on key variables. Distributions will guide modeling decisions and normalizing transformations will be used when appropriate.

Although we expect that randomization will balance the groups, we will validate randomization by comparing groups on key variables potentially related to outcomes. If we identify significant group differences, we will adjust for these variables in models. The EUC condition will be designed to be equal-attention, but we will examine potential associations of the outcomes with length of session in sensitivity models.

Mixed effects regression models (described below) will allow the use of data from all participants, including those with incomplete follow-up, and provides unbiased parameter estimates under the missing-at-random assumption.¹⁰² If the missing-at-random assumption is untenable, we will handle missing data with a pattern mixture model. Where we have missing data on individual variables for more than 15% of observations, we will impute using SAS PROC MI and PROC MIANALYZE to combine the results of PROC MI.

Generalized linear models (GLMs) and generalized linear mixed-effects models (GLMMs). We will assess treatment effects by using GLMs to examine differences between the intervention and EUC groups at specific assessment waves and GLMMs to examine the primary dependent measures over the study period as a whole. GLMMs have the advantage of: 1) adjusting variances for correlated data (i.e., repeated measures); 2) allowing time-varying independent variables; and 3) allowing subject-specific inferences. The link function for GLMs and GLMMs will be based on the distribution for each outcome. We will use procedures SAS PROC MIXED for continuous variables and PROC GLIMMIX for dichotomous and count data.

Aim-specific analyses. All hypotheses will be planned a priori. All analyses will use two-sided tests.

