Aim 1 analyses. Hypothesis 1: Participants randomized to the intervention condition will report fewer overdose risk behaviors than EUC participants at follow-up. The overdose risk behavior is conceptually a composite count of number of behaviors. However, prior to initiating modeling, we will examine the distribution of responses to individual items on the overdose risk behavior assessment as well as the distribution of the overall composite count. Primary analyses will consist of GLMs to examine group (Intervention vs. EUC) as the primary independent variable at each time point and a GLMM to examine the average effect of the intervention over all assessments. If GLM findings suggest that the impact of the intervention may vary by assessment period, this will be examined using a time by group interaction term.

Aim 2 analyses. Hypothesis 2a: Participants randomized to the intervention condition will have lower average MEM/day doses and MPRs than EUC participants over follow-up. Hypothesis 2b: Participants randomized to the intervention condition will report lower levels of aberrant OA use than EUC participants over follow-up. Aim 2 dependent variables will include both objective measures based on pharmacy data and self-reported aberrant use. Prescribed OA dose will reflect escalating doses (likely due to patient request) and high total doses after combining regularly scheduled and "as needed" OAs.¹² An MPR⁸² greater than 1 identifies potential overuse based whether new fills frequently occur before the days supplied by a prior fill have elapsed. The distribution of the daily dose, MPR, and COMM scores will be examined to select appropriate models. The same analysis strategy used to test intervention effects in GLMs and GLMMs for Aim 1 will be used for the dependent variables in Aim 2.

Secondary aim 1 analyses. Hypothesis 3: Participants randomized to the intervention condition will have fewer non-fatal overdoses, fewer injuries and other OA-related adverse events, and better OA storage and disposal behaviors and better functioning than EUC participants. Analysis will follow the general GLM and GLMM framework used in the Aims 1 and 2 analyses, but a survival analysis approach using Cox proportional hazards regression modeling will also be used to examine time-to-event data (non-fatal overdoses and emergency department visits).

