Power analysis. All power analyses are conservative because they are based on a retention rate of 80%, n=360 (180 per condition), despite the fact that the methods will maximize analytic sample size by including individuals with partial follow-up data. All power calculations were based on two-sided tests with $\alpha=0.05$ and were conducted using G*Power software. We estimated power for GLMs for both count and continuous outcomes. For continuous outcomes, such as OA dose and aberrant use (Aim 2), 80% power is achieved to detect a standardized effect size of 0.30. For overdose risk behaviors (Aim 1), we assumed a Poisson distribution and a mean count of 1.9 (based on our pilot work) and found 80% power is achieved to detect an incidence rate ratio of 0.80 for the intervention compared to EUC. We extrapolate from the power calculations presented here for GLMs that power for outcomes in GLMMs will allow for detection of similar effect sizes. Thus, the proposed study has sufficient sample size to detect small to moderate effects.

DISSEMINATION PLAN

Several dissemination products will be developed during this study. We will finalize the intervention training manual and develop additional materials. We will create a video demonstration of the different components of the intervention, with multiple examples for each component in order to show how the intervention is tailored. These products and the computer aid will be shared with key central office stakeholders and made available to VHA clinicians. Additionally, these products will be ready to be used in a future hybrid type-1 implementation study using a stepped wedge design and informed by the Replicating Effective Programs model.¹⁰⁴ This study could examine factors that facilitate implementation as well as fatal and non-fatal overdose as an outcome by implementing the intervention with larger numbers of patients.

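### Four tests of hypothesis 1 are all labelled primary and none is named as deciding; if any one may count, the favourable false-positive chance is about 4.2% to 6.5% instead of 2.5%

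*Combined protocol and SAP*

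**What the plan says.** All references are to the combined protocol and SAP.

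- **Aim 1 analyses:** "Primary analyses will consist of GLMs to examine group (Intervention vs. EUC) as the primary independent variable at each time point and a GLMM" for the average effect over all assessments. The next sentence adds a time-by-group interaction, but only if the GLM results suggest that the effect differs between assessment periods.
- **Hypothesis 1:** intervention participants "will report fewer overdose risk behaviors than EUC participants at follow-up". No wave or average is named.
- **Specific aims, Aim 1:** the comparison is "over one year of follow-up compared to patients assigned to equal attention EUC".
- **Section on GLMs and GLMMs:** GLMs compare the groups at specific waves, and "GLMMs to examine the primary dependent measures over the study period as a whole" are the other half of the approach.
- **Power analysis:** power is calculated for the GLMs. For the mixed models: "We extrapolate from the power calculations presented here for GLMs that power for outcomes in GLMMs will allow for detection of similar effect sizes".
- **Aim 2 analyses:** under hypothesis 2a, intervention participants "will have lower average MEM/day doses and MPRs than EUC participants over follow-up". Under 2b, they "will report lower levels of aberrant OA use than EUC participants over follow-up". Then: "The same analysis strategy used to test intervention effects in GLMs and GLMMs for Aim 1 will be used" for the Aim 2 variables.

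The analysis plan also says that hypotheses are set in advance and that tests are two-sided. It does not say which analysis decides, in what order the tests are taken, or how alpha is shared among them.

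**The concern.** Four tests of one hypothesis carry the same primary label. Run as written, without adjustment, they can yield a significant result at one wave while the average over the year is not significant. The plan does not say whether that is a primary success, so the choice could be made after the results are known. Aim 1 is about a year of follow-up, and a 3-month result alone would not answer it.

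The interaction sentence does not close the gap. Whether the term enters depends on the wave results, and its entry does not settle which test decides. It can also change what the group coefficient means. Under reference coding, for example, the group coefficient in a model with group-by-time is the effect at the reference wave, not the average. The plan gives neither coding nor contrast, so even a reader who takes the GLMM as deciding does not have a fixed estimate.

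**Working it through.** **Inputs from the documents.** Two-sided alpha 0.05, hence 0.025 in the direction favouring the intervention; 180 per arm (80% of 450 is 360); ORB mean count 1.9, assumed Poisson; rate ratio 0.80; standardized effect 0.30 for continuous outcomes (all from Power analysis). Follow-up at 3, 6 and 12 months (Data collection procedures). The Measures table does not list ORB at the post-test, so there are three post-baseline waves.

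**Input assumed.** The correlation r between the wave test statistics, taken as equal for all pairs at 0.5, 0.7 or 0.9.

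**Step 1: reproduce the plan's 80% power for a single-wave GLM.**
- Continuous: noncentrality 0.30 × √(180/2) = 0.30 × 9.487 = 2.846. Power = Φ(2.846 − 1.960) = 81.2%.
- ORB: SE of the log rate ratio = √(1/(180 × 1.9) + 1/(180 × 1.52)) = 0.0811. |ln 0.80| / 0.0811 = 2.751. Power = Φ(2.751 − 1.960) = 78.6%. The version with separate null and alternative variances gives 81.7%.

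Both agree with the stated 80%, and both are powers for one wave GLM.

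**Step 2: error rate if any of the four may count.** Under no effect, draw three standard normal wave statistics z₁, z₂, z₃ with common correlation r. Take the GLMM average as z̄ / √((1 + 2r)/3). Count the draws in which at least one of the four lies below −1.96 (favourable), or beyond ±1.96 (two-sided). Several million draws were used.

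| r | Any of four, favourable | Any of four, two-sided | Favourable wave, average not significant |
|---|---|---|---|
| 0.5 | 6.5% | 13.0% | 4.0% |
| 0.7 | 5.5% | 11.1% | 3.0% |
| 0.9 | 4.2% | 8.4% | 1.7% |
| One deciding test | 2.5% | 5% | – |

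The columns agree: the average alone contributes 2.5%, and 2.5 + 4.0 = 6.5, 2.5 + 3.0 = 5.5 and 2.5 + 1.7 = 4.2.

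**Step 3: sensitivity to the correlation pattern.** If correlation decays with time (r for 3–6 months, r² for 6–12, r³ for 3–12), the favourable rate is 4.8% at r = 0.9 and 7.2% at r = 0.5.

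**Step 4: cost of letting the average decide.** For an equal-weight average, noncentrality = (mean standardized effect) × 9.487 / √((1 + 2r)/3). The divisor is 0.816, 0.894 and 0.966 at r = 0.5, 0.7 and 0.9.

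| Effect at 3 / 6 / 12 months | Mean | Power at r = 0.5 | r = 0.7 | r = 0.9 |
|---|---|---|---|---|
| 0.30 / 0.30 / 0.30 | 0.30 | 94% | 89% | 84% |
| 0.30 / 0.20 / 0.10 | 0.20 | 64% | 56% | 50% |
| 0.30 / 0 / 0 | 0.10 | 21% | 18% | 16% |

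For ORB at a constant rate ratio of 0.80 under the plan's Poisson assumption, 2.751 divided by the same divisors gives 92%, 87% and 81%.

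**The case against.** The strongest reply is that the plan already implies the answer. Aim 1 speaks of a year of follow-up, the modelling section assigns the GLMM to the whole study period, and the Aim 1 analyses describe it as the average effect. The phrase in hypothesis 1 is neutral rather than contrary, and calculating power for GLMs is a shortcut, not a decision rule. A reader might infer that the documents contradict themselves here. They do not: the pointers that exist lean one way, and what is missing is the sentence that makes the lean binding.

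The reply does not remove the point. The wave GLMs are listed first among the primary analyses and are not called supportive. Hypotheses 2a and 2b specify the period over follow-up, while hypothesis 1 does not.

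A second reply is that the interaction term is a safeguard for the case where waves differ. It is a relevant formal check, but it is triggered by the data and does not name a deciding test.

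A third is that the inflation rests on an any-one-counts rule that the plan never states. That is correct. A reader might infer that the trial's error rate is 6.5%. The documents support only the conditional statement, since the inflation vanishes once one test is fixed. A reader might also imagine the opposite rule, that all four tests must agree, but nothing in the text suggests it.

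For Aim 2 the gap is smaller, because 2a already names an average over follow-up and 2b points the same way.

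**Conclusion.** The point holds for hypothesis 1: four unadjusted tests are labelled primary, and the deciding one is not named. If any one may count, the favourable false-positive chance on ORB is about 4.2% to 6.5% against 2.5%, and 8.4% to 13% two-sided against 5%. The part due to a favourable wave with a non-significant average is 1.7% to 4.0%.

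These figures rest on assumed equal wave correlations of 0.9 to 0.5, on normal approximations, and on the any-one-counts reading. They concern one outcome and are not a trial-level error rate; multiplicity across ORB, dose, MPR and COMM is a separate matter. For Aim 2, all that is needed is confirmation that the average decides. The size is modest, but the repair is nearly free and should be made before any comparison by arm.

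**What to change.** 1. **Deciding test for hypothesis 1.** State that it is the GLMM group effect on ORB averaged over the follow-up assessments, two-sided 0.05. Take it as a pre-specified contrast from a model that always contains group, time and group-by-time. This replaces the data-triggered interaction.
2. **Weights.** Fix them in advance, either equal by wave or by length of recall period. Measures says that follow-ups generally cover the time since the last assessment, so the periods are about 3, 3 and 6 months and the recall weights 1/4, 1/4 and 1/2. The choice matters if the effect fades: 0.30 / 0.20 / 0.10 averages 0.20 with equal weights and 0.075 + 0.05 + 0.05 = 0.175 with recall weights.
3. **Wave effects.** Report the 3-, 6- and 12-month effects as secondary contrasts from the same model.
4. **Aim 2.** Confirm that the average over follow-up decides. For COMM, use the same form of contrast with its weights stated; COMM asks about the past month, so the recall-length argument does not carry over. For MEM/day and MPR, use the pharmacy-based average that hypothesis 2a already names, without forcing it onto the survey waves.

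The change is wording only and needs no extra patients or data. A single-wave result can no longer stand as primary, and a fading or 3-month-only effect is harder to confirm, by the amounts in the last table of the working. It does not address multiplicity across the ORB and Aim 2 outcomes.

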Randomization. Participants will be individually randomized to receive either the intervention or EUC after completing the baseline. The coordinator will supervise the randomization, which will be conducted by the analyst, using computerized block-randomization stratified by OEF/OIF/OND status in blocks of 10.

Intervention and EUC condition delivery procedures. The intervention and EUC procedures will each take approximately 30 minutes to complete, in addition to the chronic OA therapy informed consent. These sessions will take place in a private room or over the phone in a private office to ensure privacy and confidentiality. Consistent with our prior interventions, the sessions will be computer-aided to enhance fidelity. For the intervention, the therapist uses the computer aid to progress through a series of prompts, which ensures that each step of the intervention is covered and reminds therapists of specific ME tools relevant to each step. The computer aid also includes screens with suggested options/choices that can be shared with participants who have trouble generating goals, values, strengths, and tools without prompting. The EUC condition will also use a computer aid that will include a series of prompts and non-interactive visual aids related to the content of that condition. Feedback to the participants' prescribers will be given based on the protocol developed through the process described above.

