Data collection procedures. Assessments will be self-administered paper-pencil surveys, and research staff will be available to clarify questions. There are five assessments: baseline, post-test, and 3-, 6-, and 12-month follow-up. This assessment schedule will be able to measure if intervention impacts both proximal (e.g., self-efficacy) and distal (e.g., overdose risk behavior) outcomes and to allow enough time to pass to detect less common outcomes (e.g., non-fatal overdose and emergency department visits). All assessments will occur in an area where privacy and confidentiality can be maintained and will take up to 1 hour. When the participant has limited time, the assessment may be completed over the phone. For the post-test, the study therapist will have someone else on the team complete that assessment, or schedule a time for another study member to call back the participant. This will ensure that we are collecting accurate feedback from the participants on the

intervention sessions. This length is comparable to prior research assessments at the Ann Arbor VAMC. Privacy during assessments will be achieved by making sure no one can overhear the conversation. If applicable, research staff will ask others to leave the room during interviews. Baseline assessment will occur at the time of recruitment or shortly after. After intervention or EUC procedures, participants will complete a brief post-test assessment to measure changes in knowledge, self-efficacy, and motivation. Participants will be given \$30 (+\$5 for the urine drug screen [UDS]) for completing the baseline and post-test assessments. Participants will be given an additional \$10 at each assessment to assist with travel expenses.

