Measures. Data will be collected through a combination of self-report, medical records abstraction, and UDS. In general, the baseline survey will assess past year or lifetime while the follow-up assessments will assess the period since the last assessment. For self-report data, questionnaires with established reliability and validity will be used whenever possible. Reviews suggest that self-report drug use data has a moderate to strong degree of reliability and validity.⁸⁰ The accuracy of self-reported information on substance use is enhanced when confidentiality is ensured and the interview is administered when the respondent is not intoxicated.⁸¹ The voluntary UDS will be used to improve the validity of self-reported substance use.

Measure title	Baseline	Post-Intervention	Follow-ups
Current Opiate Misuse Measure (COMM)	X		X
Overdose Risk Behaviors (ORB)	X		X
Overdose Experiences, Self –Alcohol (OESWA)	X		X
Overdose Experiences, Self and Witnessed – Drugs (OESWD)	X		X
Treatment Service Review (TSR)	X		X
Alternative Therapies (AT)	X		X
Revised Injury Behavior Checklist (RIBC)	X		X
Pain Treatment Satisfaction Scale (PTSS)	X		X
Safe Storage and Disposal of OAs	X		X
Veterans RAND 12-Item Health Survey (VR-12)	X		X
Knowledge of Overdose Risk Factors (OK)	X	X	X
Overdose Education and Naloxone Distribution (OEND)	X		X

Behavioral Intentions (BI)	X	X	X
Self-Efficacy-Overdose Self (SEOS)	X	X	X
Perceived Satisfaction and Utility (PSU – I & PSU – C)		X	
National Comorbidity Survey (NCS)	X		X
Brief Pain Inventory – Short Form (BPI)	X		X
Pain, Enjoyment and General Activity Scale (PEG)	X		X
Centrality of Pain Scale (CPS)	X		X
Addiction Severity Index (ASI)	X		X
Alcohol, Smoking and Substance Involvement Treatment (ASSIST)	X		X
Demographic information	X	X	X
Military service information (MSI) not individually labeled but included in Demographics	X		X

Outcomes. (Measured at Baseline and Follow-up, except where noted)

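### The primary GLMM does not say whether baseline is an outcome wave; if it is, a single group term keeps only about 75% of the intervention effect

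*Combined protocol and SAP*

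**What the plan says.** Under Aim 1 analyses, the primary analyses are GLMs of group at each time point plus "a GLMM to examine the average effect of the intervention over all assessments". The general GLM/GLMM paragraph describes "GLMMs to examine the primary dependent measures over the study period as a whole". If the wave-by-wave GLMs hint that the effect differs by assessment, "this will be examined using a time by group interaction term"; otherwise the default is a single group effect. Aim 2 uses the same strategy.

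The Data collection procedures section states: "There are five assessments: baseline, post-test, and 3-, 6-, and 12-month follow-up". The heading over the outcome measures reads "Measured at Baseline and Follow-up, except where noted", and the measures table shows the overdose risk behavior measure (ORB) and the opioid misuse measure (COMM) at baseline and follow-ups but not at post-test. On timing, the Randomization section says: "Participants will be individually randomized to receive either the intervention or EUC after completing the baseline".

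The questions themselves concern follow-up. Hypothesis 1 reads "Participants randomized to the intervention condition will report fewer overdose risk behaviors than EUC participants at follow-up", Hypotheses 2a and 2b refer to the follow-up period, and Aims 1 and 2 are framed "over one year of follow-up compared to patients assigned to equal attention EUC".

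The only stated route for a baseline variable into a model is adjustment when the groups differ significantly on it.

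**The concern.** The sentence that defines the longitudinal model does not list the waves it covers. ORB and COMM are measured at four of the listed assessments, and baseline is one of them. An analyst could therefore enter baseline as a response row with one group term and still comply with the text. Randomization follows baseline, so the true group difference there is zero, and the coefficient would average one null wave with three post-intervention waves. That contrast is smaller than the one Hypothesis 1 asks about. A second analyst could use only 3, 6 and 12 months and comply equally well. The two would report different effects from the same data, in the only primary analysis that uses all the waves.

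**Working it through.** **Inputs from the documents.** 225 randomized per arm; 180 per arm in the power section (80% retention); two-sided alpha 0.05; 0.30 SD for continuous outcomes; IRR 0.80 at a mean count of 1.9 (Poisson) for overdose risk behaviors; outcomes at baseline, 3, 6 and 12 months. **Assumed:** within-person correlation r between waves, equal for all pairs, at 0.3, 0.5 and 0.7. The documents give no value.

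**1. The plan's own power figures.**
- Continuous: SE = √(2/180) = 0.1054; 0.30/0.1054 = 2.846; power = Φ(2.846 − 1.960) = 81%.
- Count: SE of log IRR = √(1/(180×1.9) + 1/(180×1.9×0.8)) = 0.0811; |ln 0.80|/0.0811 = 2.751; power = Φ(0.791) = 79%.

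Both agree with the stated 80%. They are single-wave calculations; the power section extrapolates to the GLMM without computing it.

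**2. Share of the effect kept if baseline is an outcome row.** With complete data, four waves and one group term, the expected coefficient is (0 + δ + δ + δ)/4 = 0.75δ.
- Continuous: 0.75 × 0.30 = 0.225 SD.
- Count: 0.80^0.75 = 0.846 on the log scale; (1 + 3×0.80)/4 = 0.850 on the mean scale.

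Dropout raises the weight of baseline. A simulated random-intercept model (225 per arm, retention falling evenly to 80% at 12 months, 1,500 runs per setting) gave 0.204 to 0.211 SD for a true 0.30, so 68% to 70% is kept. On the log scale, 0.80^0.70 = 0.855. With baseline left out, the same simulation returned 0.30 SD.

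**3. Power at 0.30 SD, 180 per arm, complete waves.** The variance of the group coefficient is (2/180)(1+3r)/4 with baseline pooled and (2/180)(1+2r)/3 with follow-up only.

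| r | Baseline pooled: 0.225/SE | Power | Follow-up only: 0.30/SE | Power |
|---|---|---|---|---|
| 0.3 | 0.225/0.0726 = 3.10 | 87% | 0.30/0.0770 = 3.90 | 97% |
| 0.5 | 0.225/0.0833 = 2.70 | 77% | 0.30/0.0861 = 3.49 | 94% |
| 0.7 | 0.225/0.0928 = 2.42 | 68% | 0.30/0.0943 = 3.18 | 89% |

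The simulation with 225 per arm and 80% retention at 12 months gave 88%, 78% and 67% against 99%, 96% and 93%.

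**4. The other reading: baseline not used.** There is then no dilution, but available precision is left unused. Under the same correlation structure, adjusting for baseline lowers the variance factor of the follow-up mean from (1+2r)/3 to (1+2r)/3 − r². At r = 0.3, 0.5 and 0.7 this is 0.533 to 0.443, 0.667 to 0.417, and 0.800 to 0.310: reductions of 17%, 38% and 61%. The gain is smaller if baseline correlates less with follow-up than the follow-ups do with each other.

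**5. Recall windows.** The Measures section says baseline generally covers the past year or lifetime, and follow-ups the time since the last assessment. If baseline counts were 1.5 or 2 times the follow-up level (assumed), the pooled ratio on the mean scale would be (1.5 + 2.4)/4.5 = 0.87 or (2 + 2.4)/5 = 0.88.

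**The case against.** A reader might infer that the plan's primary analysis is diluted by a quarter as it stands. The documents do not support that. No passage makes baseline an outcome row. The aims and hypotheses point to follow-up, and an intervention given after baseline has no effect there to average. The list of five assessments cannot be applied literally, because it includes a post-test at which ORB and COMM are not collected. The differing recall windows also make baseline an unnatural fourth wave. The power section speaks of participants with partial follow-up and expects the GLMM to detect effects similar to the single-wave GLMs, which fits a follow-up-only model. The follow-up GLMs are also primary and carry no dilution. If GLMs were run at baseline too, a null there beside effects later is the pattern that would prompt the interaction term.

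All of this stands against calling the dilution a property of the plan. It does not settle which rows enter the model. Removing the post-test from the list removes a wave without outcome data; baseline has outcome data. The plan also credits mixed models with using every participant, including those with incomplete follow-up, and someone with no follow-up at all contributes only if baseline is a response. The interaction term has no stated trigger, and the plan does not define the average effect once it is added.

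**Conclusion.** The ambiguity is certain; the dilution is conditional on baseline being modelled as a response with one unconstrained group term. In that case about a quarter of the effect is lost with complete data and about 30% with 80% retention at 12 months. The power loss depends on the assumed correlation. At the planned 0.30 SD and 180 per arm it is roughly 10 points at r = 0.3 and 21 points at r = 0.7. At r = 0.5 the diluted analysis still has 77% power, close to the planned 80%, so it would be too strong to say that the trial would miss its planned effect. I give no power figure for the count outcome: the pilot SD of 2.0 at a mean of 1.9 implies variance 4.0 against a Poisson 1.9, and any figure would mix that separate issue with the dilution.

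This is a free improvement: it removes the dilution on one reading and gains precision on the other.

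**What to change.** Add to the Aim 1 analysis text, and carry to Aim 2 and the other analyses that reuse the framework:

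- The GLMM treatment contrast covers the 3-, 6- and 12-month assessments only.
- The baseline value of the outcome enters either as a covariate, or as a response with the arms constrained equal at baseline and that wave excluded from the contrast.
- Visit is in the model as a categorical term, with group-by-visit terms at follow-up included from the start. The average effect is the equal-weight mean of the three follow-up contrasts. This replaces adding the interaction only when the wave-specific GLMs point to it.

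A single group term over the three follow-up waves would also answer Hypothesis 1. The equal-weight mean is preferred because its weights do not shift with dropout.

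The cost is a few sentences, written before follow-up outcomes are analysed by arm. Data collection and sample size do not change.
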